#### 6.4. PROTOCOL DEVIATIONS

Any deviation from protocol will be listed by subject and date. The type of deviation along with a description and any additional comments about the deviation will be listed.

# 7. CHANGES IN THE PLANNED ANALYSES

An analysis of the number of doses of antipyretic medications will be prepared.

There are no further changes anticipated to the protocol specified analyses. Should any more deviations occur, these changes will be fully described in the Clinical and Statistical Report.

# 8. REVISION HISTORY

Date	Revision	Rationale
29JUN2016	Clarification of units for age based on cohort and imputation methods for missing symptom scores. Addition of virology population. Removal of analyses for time weighted area under the curve for TCID 50 . Changed imputation method to last	Incorporation of review comments from BioCryst.
	observation carried forward.	

# 9. **PROGRAMMING CONVENTIONS**

- Page orientation, margins, and fonts: Summary tables, listings, and figures will appear in landscape orientation. There should be a minimum of a 1.25" boundary on the upper (bound) edge, and a minimum of a 1.0" boundary on the remaining three edges. Output should be printed in Courier New with a point size of 8. Titles may be printed using a larger font (e.g., Arial point size 10).
- Identification of analysis population: Every summary table and figure should clearly specify the analysis population being summarized. Listings will be prepared for all subjects randomized.
- Group headers: In the summary tables, the group headers will identify the treatment group and the within-group sample size for the indicated analysis population. Of note, the header's sample size does not necessarily equal the number of subjects actually summarized within any given summary module; some subjects in the analysis population may have missing values and thus may not be summarized.
- Suppression of percentages corresponding to null categories: When count data are presented as category frequencies and corresponding percentages, the percent should be suppressed when the count is zero in order to draw attention to the non-zero counts.
- Presentation of sample sizes: Summary modules should indicate, in one way or another, the number of subjects actually contributing to the summary statistics presented in any given summary module. As mentioned above, this may be less than the number of subjects in the analysis population.
  - ♦ In the quantitative modules describing continuous variables (and thus presenting sample size, means, and standard deviations), the sample size should be the number of non-missing observations
  - For categorical variables that are presented in frequency tables, the module should present the total count in addition to the count in each category. Percentages should be calculated using this total as the denominator, and the percentage corresponding to the sum itself (that is, 100%) should be presented so as to indicate clearly to a reviewer the method of calculation.
- Sorting: Listings will be sorted by treatment group, subject number and date, if applicable. If a listing is sorted in a different manner, a footnote will indicate as such.
- General formatting rules: Rounding for all variables will occur only as the last step, immediately prior to presentation in listings, tables, and figures. No intermediate rounding will be performed on derived variables. The standard rounding practice of rounding numbers ending in 0-4 down and numbers ending in 5-9 up will be employed.
- The presentation of numerical values will adhere to the following guidelines:

- Raw measurements will be reported to the number of significant digits as captured electronically or on the CRFs.
- Standard deviations will be reported to one decimal place beyond the number of decimal places the original parameter is presented.
- Means will be reported to the same number of significant digits as the parameter.
- Calculated percentages will be reported with no decimals.
- Dates will be formatted as DDMMMYYYY. Partial dates will be presented on data listings as recorded on CRFs.
- Time will be presented according to the 24-hour clock (HH:MM).

# 10. PROPOSED TABLES, LISTINGS, AND FIGURES FOR FINAL ANALYSIS

Output Number	Output Title
Table 14.1.1	Subject Follow-Up and Termination from Study; Intent-to-Treat Population
Table 14.1.2.1	Randomization, Eligibility, and Treatment Status; Intent-to-Treat Population
Figure 14.1.2.2	BCX1812-305 Study Population Disposition; Intent-to-Treat Population
Table 14.1.3	Demographics and Baseline Characteristics; Intent-to-Treat Population
Table 14.1.4	Populations for Analysis; Intent-to-Treat Population
Table 14.1.5	Summary of Subject Diary Completion; Intent-to-Treat-Infected Population
Table 14.2.1.1	Summary of Oral Temperature; Intent-to-Treat Infected Population
Table 14.2.1.2.1.1	Time to Resolution of Fever; Intent-to-Treat Infected Population
Figure 14.2.1.2.1.2	Time to Resolution of Fever (Kaplan-Meier Plot); ITTI Population
Figure 14.2.1.2.1.3	Median (95% CI) Time to Resolution of Fever; ITTI Population
Table 14.2.1.2.2	Time to Resolution of Fever by Viral Sub-Type; Intent-to-Treat Infected Population
Table 14.2.2.1.1.1	Time to Alleviation of Symptoms [1]; Intent-to-Treat Infected Population
Figure 14.2.2.1.1.2	Time to Alleviation of Symptoms (Kaplan-Meier Plot); ITTI Population
Figure 14.2.2.1.1.3	Median (95% CI) Time to Alleviation of Symptoms; ITTI Population
Table 14.2.2.1.2.1	Time to Alleviation of Symptoms [1] by Viral Sub-Type; Missing Values are Censored at the Last Available Assessment; Intent-to-Treat Infected Population

Output Number	Output Title
Figure 14.2.2.1.2.2	Median (95% CI) Time to Alleviation of Symptoms by Viral Sub- Type; ITTI Population
Table 14.2.3.1.1.1	Summary of Changes $\log_{10}$ Tissue Culture Infective Dose 50 (TCID 50 /mL) by Study Visit; Intent-to-Treat Infected Population
Figure 14.2.3.1.1.2	Box Plots of Viral Titers ( $TCID_{50}$ /mL) by Study Visit; Subjects with Negative Baseline Viral Titers are Excluded; Intent-to-Treat Infected Population
Figure 14.2.3.1.1.3	Histograms of Viral Titers ( $TCID_{50}$ /mL) by Study Visit; Subjects with Negative Baseline Viral Titers are Excluded; Intent-to-Treat Infected Population
Figure 14.2.3.1.1.4	Median (with IQR) Change from Baseline Viral Titers (TCID 50 /mL) by Study Visit; Subjects with Negative Baseline Viral Titers are Excluded; Intent-to-Treat Infected Population
Table 14.2.3.1.2	Summary of Changes $\log_{10}$ Tissue Culture Infective Dose 50 (TCID 50 /mL) by Study Visit and Viral Sub-Type; Intent-to-Treat Infected Population
Table 14.2.3.2.1	Summary of Viral Shedding by Study Visit; Intent-to-Treat Infected Population
Table 14.2.3.2.2	Summary of Viral Shedding by Study Visit and Viral Sub-Type; Intent-to-Treat Infected Population
Table 14.2.3.3.1	Summary of RT-PCR Result by Study Visit; Intent-to-Treat Infected Population
Table 14.2.3.3.2	Summary of RT-PCR Result by Study Visit and Viral Sub-Type; Intent-to-Treat Infected Population
Table 14.2.3.4	Change of Influenza Virus Susceptibility to Neuraminidase Inhibitors by Viral Subtype; Intent-to-Treat Infected Population
Table 14.2.4	Summary of Influenza-Related Complications; Intent-to-Treat Infected Population

Output Number	Output Title
Table 14.2.5	Number of Doses of Antipyretic Medications; Intent-to-Treat Infected Population
Table 14.2.6	Summary of Subject-Rated Assessment of Ability to Perform Daily Activities; Intent-to-Treat Infected Population
Table 14.2.7	Summary of Assessment of Appetite and Eating Patterns; ITTI Population
Table 14.3.1.1	Treatment-Emergent Adverse Events by System Organ Classification, Preferred Term and Greatest Severity; Safety Population
Table 14.3.1.2	Treatment-Emergent Adverse Events Possibly, Probably, or Definitely Related to Study Drug by System Organ Classification and Preferred Term; Safety Population
Table 14.3.1.3	Treatment-Emergent Serious Adverse Events by System Organ Classification and Preferred Term; Safety Population
Table 14.3.1.4	Treatment-Emergent Adverse Events Leading to the Discontinuation of Study by System Organ Classification and Preferred Term; Safety Population
Table 14.3.5.1	Summary of Select Laboratory Values by Study Visit; Safety Population
Table 14.3.5.2	Graded Laboratory Toxicities; Safety Population
Table 14.3.5.3.1	Laboratory Shifts from Baseline: Chemistry; Safety Population
Table 14.3.5.3.2	Laboratory Shifts from Baseline: Hematology; Safety Population
Table 14.3.5.3.3	Laboratory Shifts from Baseline: Urinalysis; Safety Population
Table 14.3.6	Summary of Vital Signs by Study Visit; Safety Population
Table 14.3.7	Abnormal Physical Examinations; Safety Population
Table 14.3.8	Concomitant Medications by Generic Name and Drug Classification; Safety Population

Output Number	Output Title
Table 14.4.1.1	Summary of Plasma Concentrations of Peramivir by Time point; Intent-to-Treat Population
Table 14.4.1.2	Summary of Plasma Concentrations of Peramivir; Exposure Response Population
Figure 14.4.2	Relationship between Time to Alleviation of Influenza Symptoms and Peramivir Plasma Concentrations at 30-60 Minutes Post-Dose; Exposure-Response Population
Figure 14.4.3	Relationship between Viral Change from Baseline and Peramivir Plasma Concentrations at 30-60 Minutes Post-Dose; Exposure-Response Population
Listing 16.2.1	Study Completion; Intent-to-Treat Population
Listing 16.2.2	Protocol Deviations; Intent-to-Treat Population
Listing 16.2.4.1	Inclusion/Exclusion Criteria; Intent-to-Treat Population
Listing 16.2.4.2	Subject Eligibility and Randomization; Intent-to-Treat Population
Listing 16.2.4.3	Demographics; Intent-to-Treat Population
Listing 16.2.4.4	Medical History; Intent-to-Treat Population
Listing 16.2.4.5	Prior and Concomitant Medications; Intent-to-Treat Population
Listing 16.2.5.1	Study Medication Administration; Intent-to-Treat Population
Listing 16.2.5.2	Pharmacokinetic Sample Collection Time and Concentrations; PK Population
Listing 16.2.6.1.1	Summary of Efficacy Variables; ITTI Population
Listing 16.2.6.2	Influenza Symptoms; Intent-to-Treat Population
Listing 16.2.6.3	Temperature; Intent-to-Treat Population
Listing 16.2.6.4	Subject-Rated Assessment of Daily Activities and Assessment of Appetite and Eating Patterns; Intent-to-Treat Population

Output Number	Output Title
Listing 16.2.6.5	Viral Titers and Viral Susceptibility; Intent-to-Treat Population
Listing 16.2.6.6	RT-PCR for Influenza; Intent-to-Treat Population
Listing 16.2.6.7	Symptom Relief Medications; Intent-to-Treat Population
Listing 16.2.6.8	Influenza-Related Complications; Intent-to-Treat Population
Listing 16.2.7	Adverse Events; Intent-to-Treat Population
Listing 16.2.8.1.1	Laboratory Tests - Hematology; Intent-to-Treat Population
Listing 16.2.8.1.2	Laboratory Tests - Chemistry; Intent-to-Treat Population
Listing 16.2.8.1.3	Laboratory Tests - Urinalysis; Intent-to-Treat Population
Listing 16.2.8.1.4	Laboratory Tests - Virology; Intent-to-Treat Population
Listing 16.2.8.1.5	Laboratory Tests - Other; Intent-to-Treat Population
Listing 16.2.8.2	Blood and Urine Collection and Pregnancy Tests; Intent-to-Treat Population
Listing 16.2.8.3	Vital Signs, Height, and Weight; Intent-to-Treat Population
Listing 16.2.8.4	Physical Examinations; Intent-to-Treat Population
Listing 16.2.9.1	Changes in NA Amino Acids from Baseline to Post-Baseline
Listing 16.2.9.2	Changes in HA Amino Acids from Baseline to Post-Baseline
Listing 16.2.9.3	NA Sequence Alignment
Listing 16.2.9.4	HA Sequence Alignment

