7. INVESTIGATIONAL PLAN

7.1. Endpoints

7.1.1. Primary Endpoint

The primary endpoints of this study will be assessment of adverse events, laboratory analyses (clinical chemistry, hematology and urinalysis), vital signs and physical examinations.

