11.2.3. Urinalysis

Routine urinalysis evaluations will include dipstick evaluations for protein, glucose, ketones, hemoglobin, and specific gravity. If indicated by dipstick results, the urine should be sent for microscopy.

Urinalysis will be conducted on urine samples obtained at Baseline, and at the Day 7 follow-up assessment. Clinically significant results should be reported as AEs.

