13.9. Safety Analyses

Adverse Events will be mapped to a Medical Dictionary for Regulatory Activities (MedDRA)-preferred term and system organ classification. The occurrence of treatment-emergent AEs (TEAEs) will be summarized by age group and treatment group using MedDRA-preferred terms, system organ classifications, and severity. All AEs will be listed for individual subjects showing both verbatim and preferred terms. Separate summaries of treatment-emergent SAEs and AEs related to study drug will be generated.

Descriptive summaries of vital signs and clinical laboratory results will be presented by age group, treatment group and study visit. Laboratory abnormalities will be graded according to the DAIDS Table for Grading Adverse Events for Adults and Pediatrics (Publish Date: December 2004 Clarification, 2009, see Appendix 1). The number and percentage of subjects experiencing treatment-emergent graded toxicities will be summarized by age group and treatment group. Laboratory toxicity shifts from baseline to post-baseline assessments will be summarized by age group and treatment group.

Previous and concomitant medications will be mapped to a WHO preferred term and drug classification. The number and percent of subjects taking concomitant medications will be summarized using preferred terms and drug classifications.

The number and percent of subjects experiencing influenza related complications will be summarized by age group and treatment group.

Subject disposition will be presented for all subjects. The number of subjects who completed the study and discontinued from the study will be provided. The reasons for early discontinuation also will be presented.

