#### **6.3.3.** Clinical Laboratory Assessments

Descriptive summaries of the following selected (quantitative) clinical laboratory results will be presented by study visit and treatment group for each age group and overall: ALT, AST, Serum Creatinine, BUN, HGB, Albumin, and Alkaline Phosphatase. Laboratory abnormalities (toxicities) will be graded according to the DAIDS Table for Grading Adverse Events for Adults and Pediatrics (Publish Date: December 2004). The number and percentage of subjects experiencing treatment-emergent graded toxicities will be summarized by treatment group for each age group and overall. Laboratory toxicity shifts from baseline to Day 7 will be summarized by treatment group for each age group and overall.

All laboratory toxicities that occurred before the initiation of study treatment or more than 14 days post study drug discontinuation will be excluded from the tables but will be included in the listings.

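### Urinalysis shifts are summarized only as DAIDS grades, but only one of the five dipstick items (protein) can be graded directly, and three have no DAIDS row at all

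*SAP*

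**What the plan says.** Protocol 7.1.1 names urinalysis among the trial's main safety measures: "The primary endpoints of this study will be assessment of adverse events, laboratory analyses (clinical chemistry, hematology and urinalysis), vital signs and physical examinations".

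Protocol 11.2.3 sets out what is collected: "Routine urinalysis evaluations will include dipstick evaluations for protein, glucose, ketones, hemoglobin, and specific gravity". Microscopy is conditional: "If indicated by dipstick results, the urine should be sent for microscopy". On timing: "Urinalysis will be conducted on urine samples obtained at Baseline, and at the Day 7 follow-up assessment". The same section asks for clinically significant results to be reported as adverse events.

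SAP 6.3.3 sets the scale, "Laboratory abnormalities (toxicities) will be graded according to the DAIDS Table for Grading Adverse Events for Adults and Pediatrics", and the form of the shift summary, "Laboratory toxicity shifts from baseline to Day 7 will be summarized by treatment group for each age group and overall". Protocol 13.9 uses the same basis: "Laboratory toxicity shifts from baseline to post-baseline assessments will be summarized by age group and treatment group". SAP Section 10 then lists three shift tables, for chemistry, hematology and urinalysis. The last is Table 14.3.5.3.3, "Laboratory Shifts from Baseline: Urinalysis; Safety Population". No basis other than toxicity grade is stated for it.

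For descriptive summaries by visit, SAP 6.3.3 names seven analytes: ALT, AST, serum creatinine, BUN, HGB, albumin and alkaline phosphatase. Protocol 13.9 plans descriptive summaries of clinical laboratory results without limiting them to a subset.

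**The concern.** A grade-shift table can show only what the scale grades. If most urine items have no grade, a table titled as urinalysis shifts holds little more than protein, and its title does not tell the reader so. A new positive dipstick for glucose or ketones would leave no trace in it. A reader could take a nearly empty table as evidence of no urinary change when several items could not enter it.

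This matters more because urinalysis is a named primary-endpoint component and the analysis is entirely descriptive: the tables are the result, and no test or model picks up what they omit.

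The second difficulty is hematuria. Its lower DAIDS grades need a red cell count, and the protocol obtains one only when the dipstick prompts it. A child with a clean baseline dipstick has no baseline count, and the SAP does not say what baseline grade that child carries.

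**Working it through.** The documents state no figure to reproduce. The check matches items to grading rows and then follows one child through the SAP's rules.

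**Step 1. Match the dipstick items (Protocol 11.2.3) to the urinalysis rows of the DAIDS table (Protocol Appendix 1).**

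| Dipstick item | DAIDS urinalysis row | Graded from the dipstick? | Any route to a grade? |
|---|---|---|---|
| Protein | Proteinuria, random: 1+, 2-3+, 4+ for Grades 1 to 3 | Yes | Yes |
| Hemoglobin | Hematuria: 6–10 RBC/HPF (Grade 1), more than 10 (Grade 2), gross blood or RBC casts (Grade 3), transfusion (Grade 4) | No | Through microscopy, or as gross hematuria |
| Glucose | None; the DAIDS glucose rows are for serum | No | No |
| Ketones | None | No | No |
| Specific gravity | None | No | No |

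- Graded directly: 1 of 5 (1/5 = 20%).
- Dipstick result itself has no grade: 4 of 5 (80%).
- No route to any grade: 3 of 5 (60%).

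**Step 2. Look for another laboratory table.** None of the seven analytes in the SAP 6.3.3 descriptive summary is a urine item: 0 of 7. Table 14.3.5.2 (graded toxicities) has the same limit as the shift table. What remains is Listing 16.2.8.1.3, which carries the individual results, and adverse event tables 14.3.1.1 to 14.3.1.4 for results the investigator judges clinically significant.

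**Step 3. Compare with the protocol.** Protocol 13.9 does not confine descriptive laboratory summaries to selected analytes, and SAP Section 6 defines descriptive statistics to include frequencies and percentages for categorical data. Dipstick categories fit that definition. SAP Section 7 declares one change, the analysis of antipyretic doses, and says no others are anticipated. The narrowing to seven blood analytes is therefore not declared.

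**Step 4. Follow one child with new hematuria.** Baseline dipstick negative for blood, no microscopy. At Day 7 the dipstick is positive and microscopy shows a count in the Grade 1 range.

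| Reading of the baseline | Table 14.3.5.2 | Table 14.3.5.3.3 |
|---|---|---|
| Grade 0 | Treatment-emergent: rise of one grade | Shift from 0 to 1 |
| Missing | Treatment-emergent: under SAP 4.3.8, any graded value counts when baseline and screening are missing | Not specified: a missing-baseline row, or omission |

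The treatment-emergent count is the same under both readings; only the shift table depends on the choice. SAP 4.3.4 imputes nothing beyond what it specifies, and SAP Section 9 says subjects with missing values may go unsummarized. Omission is thus a possible reading, but the SAP does not prescribe it.

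**Step 5. Check for the same gap elsewhere.** Protocol 11.2.2 collects a blood count with differential. The DAIDS hematology block has no eosinophil row, so eosinophils cannot enter the hematology shift table by grade. Protocol 5.3.2.1 reports increased eosinophil count as an adverse event in 7.7% of children in the Japanese pediatric study, so the item is not idle.

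**The case against.** The strongest case against the point has four parts.

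**Hematuria is not lost.** A reader might infer that new hematuria necessarily drops out for want of a baseline grade. The documents do not support this. The missing-baseline rule in SAP 4.3.8 keeps such a child as treatment-emergent, nothing excludes the child from the shift table, and treating an unprompted microscopy as Grade 0 is a natural programming choice. Gross hematuria is Grade 3 without any red cell count. Nor do the documents give a rate of new hematuria from which to count affected children. What stands is that no rule is stated, so Tables 14.3.5.2 and 14.3.5.3.3 could disagree about the same child.

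**Other routes exist.** Clinically significant urine findings go to the adverse event tables, and every result is listed. This is correct, so urinalysis does not reach the tables through grades alone. But the adverse event route depends on investigator judgment, in an open-label study, and a listing is not a summary of a primary-endpoint component.

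**Renal safety is covered.** Creatinine and BUN are summarized by visit, creatinine is graded, and protein is gradable from the dipstick. A reader might also infer a urinary toxicity signal from the statement in Protocol 9.1 that elimination is nearly all renal. That is a pharmacokinetic statement and no such signal follows. The point rests on the primary endpoint, not on suspected renal harm.

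**A standard scale is a legitimate choice.** It is, and protocol and SAP agree on it. It works where a row exists; the difficulty is confined to items without one.

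**Conclusion.** The point holds as a gap in how a primary-endpoint component is tabulated. With the SAP followed as written, urine glucose, ketones and specific gravity (3 of 5 items) can enter no laboratory summary table. Blood can enter only through microscopy or as gross hematuria, and protein alone is graded directly. The departure from the broader laboratory summary in Protocol 13.9 is not declared in SAP Section 7.

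On hematuria the finding is limited to an unstated rule: new cases can be left out of the shift table while counted in Table 14.3.5.2, depending on how a negative baseline dipstick is coded.

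This rests on two assumptions: that Table 14.3.5.3.3 follows SAP 6.3.3, since Section 10 gives titles without shells, and that HGB in the descriptive list means blood hemoglobin. The trial tests no hypothesis and no conclusion is overturned. It is a worthwhile improvement at almost no cost.

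**What to change.** In SAP 6.3.3 and the table shells:

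1. Build Table 14.3.5.3.3 as baseline-to-Day 7 shifts in the recorded dipstick category for protein, glucose, ketones and hemoglobin, by treatment group, for each age group and overall. Show specific gravity as low, normal or high against the reference range.
2. State that a negative hemoglobin dipstick without microscopy is Grade 0 hematuria, and apply this in both Table 14.3.5.2 and any graded hematuria shift.
3. For other collected analytes with no DAIDS row, such as eosinophils, use low/normal/high shifts against the laboratory reference range.
4. Keep DAIDS grading wherever a row exists.

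The cost is a few sentences of SAP text and revised shells for existing shift tables. No new data are needed: urine is already tested at Baseline and Day 7, and the results are already planned for Listing 16.2.8.1.3. The one thing to confirm is that the database holds the dipstick results as recorded categories.
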